4.1.2 Study Treatment phase (Week 0 to Week 16)

At the baseline (week 0) visit, subjects who have met all of the inclusion and none of the exclusion criteria will be randomized using a 1:1 randomization scheme that will be regulated centrally through the UPMC IDS. Each patient enrolling in the study will be assigned an ID. At week 0 patients will undergo assessment of Raynaud activity/severity and noninvasive vascular imaging.

Patients will have a visit at week 8 to assess safety, tolerability and adverse effects of the study drug. Raynaud activity/severity and DU will be assessed.

Patients will have a final end of study visit at week 16 to assess safety, tolerability and adverse effects of the study drug. They will also undergo assessment of Raynaud activity/severity and noninvasive vascular imaging.

Dose Interruptions

If treatment is interrupted for any reason the following rules should be applied:

- ≤ 14 consecutive days without treatment it is at the discretion of the investigator if the study medication can be restarted
- >14 consecutive days without treatment: withdraw the subject from study medication.

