7.1.1 Tabulated overview**Schedule of events**

Assessment Window (days)	Screening	Baseline	Week 8 +/- 7	Week 16 +/- 7
Window				
Informed Consent	X			
Complete Medical History	X			
Physical Exam		X		X
Randomization		X		
Concomitant Medications	X	X	X	X
Adverse Events		X	X	X
Urine pregnancy test	X	X	X	X
Liver function tests, Creatinine w/ GFR	X	X	X	X
CPK		X	X	X
Fasting lipid panel, C-reactive protein, C3, C4		X		X
Vascular studies:				
EndoPAT (ischemia and post-NTG)		X		X
Laser Speckle Contrast Imaging (ischemia and post-NTG)		X		X
Brachial FMD (ischemia and post-NTG)		X		X
Questionnaires: RCS, Raynauds and Digital Ulcer VAS	X	X	X	X
Questionnaires: PROMIS and SHAQ	X	X	X	X
Digital Ulcer Count	X	X		X
Biomarker (serum, plasma) and cEPC assessment		X		X
Nitrite Analysis		X		X

* VCAM, ICAM, E-selectin, p-selectin, endothelin-1 (ET-1), VEGF, VEGF), angiotensin -1 and -2, interleukin-2, interleukin-13

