7.1.2.3 Visit 2: 8 weeks

- Assessment of Raynaud and digital ulcer activity and severity (questionnaire)
- Digital ulcer assessment
- Questionnaires
 - SHAQ
 - PROMISE-29
- Recording and assessment of AEs (see Section 7.5)
- Blood samples for safety (LFTs, CPK)
- Pregnancy test (urine) for all women of childbearing potential (Visit 3 and Visit 5) (see Section 7.5.2)
- Concomitant therapy

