7.1.2.5 Premature discontinuation of study drug treatment

In the event of premature discontinuation of study drug treatment, subjects must undergo the same procedures as outlined for the Week 16 end of study visit if they have completed 8 weeks or more of therapy. If subjects discontinue prior to 8 weeks of therapy, then they will undergo the same procedures as outlined for Week 8. All subjects who discontinue study drug treatment early will have an additional 30 day safety follow-up visit.

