8.1 General considerations

An intention to treat analysis will be performed including all who receive one dose of drug. Initial analysis will describe the baseline population, sociodemographic and clinical characteristics, and compare by treatment group. Means of continuous measures will be conducted using a t-test or Wilcoxon test and discrete measures compared with a chi-square test. The goal of all trial analyses is to provide effect size estimates for design of a later phase 3 clinical trial of statin therapy in early diffuse SSc, if deemed appropriate. If not mentioned otherwise, all statistical tests will be performed with a type I two-sided error rate of $\alpha=5\%$.

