8.2.2 Efficacy

The primary outcome of interest is the change in the EndoPAT measured RHI between baseline and week 16 between the atorvastatin and placebo group. A t-test will be used to compare the mean levels between the two groups. If differences in baseline characteristics across treatment groups are identified, multivariable linear regression models will be used to estimate the independent effect of treatment after controlling for the possible confounding variables.

The secondary outcomes of interest include the following:

- 1) Change in RCS
- 2) Change in Raynaud VAS
- 3) Change in reperfusion peak between the atorvastatin and placebo groups.
- 4) Change in reperfusion nadir between the atorvastatin and placebo groups.
- 5) Change in brachial FMD between baseline and week 16 between the atorvastatin and placebo group.

A t-test will be used to compare the mean change in RCS and Raynaud VAS between weeks 16 and baseline in the placebo and atorvastatin therapy groups. The means of reperfusion peak and nadir between groups will be calculated and a 95% confidence interval of the difference between means generated. A t-test will be used to compare the mean change in brachial FMD between baseline and week 16 between the two treatment groups.

For all of the above, assumptions of all tests (e.g., normality of residuals) will be evaluated. If violations are identified, transformations will be investigated. If adequate transformations cannot be identified, then nonparametric methods will be used.

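### RCS and Raynaud VAS: the planned unadjusted t-test on week-16 change uses the collected baseline inefficiently and leaves the week-8 scores unused

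*Combined protocol and SAP*

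**What the plan says.** Section 8.2.2 names one analysis for these outcomes: "A t-test will be used to compare the mean change in RCS and Raynaud VAS between weeks 16 and baseline", by treatment group. If test assumptions fail, transformations are tried first: "If adequate transformations cannot be identified, then nonparametric methods will be used". The same section allows multivariable regression, but only if baseline differences between groups are found, and that sentence sits with the primary RHI outcome.

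The schedule of events (Section 7.1.1) marks the row "Questionnaires: RCS, Raynauds and Digital Ulcer VAS" at screening, baseline, week 8 and week 16. Section 4.1.2 agrees for week 8: "Raynaud activity/severity and DU will be assessed".

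For early stopping, Section 7.1.2.5 assigns the Week 16 procedures to anyone with at least 8 weeks on treatment. For the others: "If subjects discontinue prior to 8 weeks of therapy, then they will undergo the same procedures as outlined for Week 8". After that, only a 30-day safety visit is stated.

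Section 8.1 sets the population: "An intention to treat analysis will be performed including all who receive one dose of drug". It also says that the analyses exist to supply effect size estimates for a phase 3 design. Section 8 gives no rule for missing values and none for assigning early-termination assessments to a visit.

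**The concern.** Subtracting the baseline fixes its coefficient at 1. When baseline and follow-up are imperfectly correlated, that over-corrects and leaves avoidable noise in the comparison. A regression coefficient estimated from the data removes it. In a 30-person pilot whose stated product is effect sizes, wider intervals for the two Raynaud symptom outcomes are a direct cost.

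The week-8 scores raise a second, smaller matter. A participant with a post-baseline score but no week-16 score cannot enter a t-test on week-16 change unless a value is supplied. If loss depends on how the participant was doing at week 8, a comparison of those who remain can be biased.

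**Working it through.** **The plan's own figure.** Section 8.4 gives a half-width of 0.374 for a 95% CI with 15 per arm. The t-based formula reproduces it: 2.048 × SD × √(2/15) = 0.374 if SD = 0.50. That SD is back-solved and not stated. The figure names no outcome and assumes that all 30 contribute. There is no precision figure for RCS or Raynaud VAS, so the rest is in relative terms.

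**Inputs.** n = 15 per arm (Section 8.4). Assumed: equal SD σ at each visit, equal correlation ρ between visits, and 10-20% loss after week 8.

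**Baseline adjustment, no loss.**
- Change score: variance of the difference = 2σ²(1 − ρ) × 2/n.
- ANCOVA: σ²(1 − ρ²) × 2/n × [1 + 1/(2n − 4)]. The bracket is the cost of estimating the slope, 1 + 1/26 = 1.038.
- SE ratio = √[(1 + ρ)/2 × 1.038].

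| ρ | (1 + ρ)/2 | SE ratio | SE reduction |
|---|---|---|---|
| 0.3 | 0.65 | 0.822 | 17.8% |
| 0.5 | 0.75 | 0.883 | 11.7% |
| 0.7 | 0.85 | 0.940 | 6.0% |
| 0.9 | 0.95 | 0.993 | 0.7% |

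At ρ = 0.5 the variance ratio is 0.75 × 1.038 = 0.779, which is worth 15/0.779 ≈ 19 per arm under the t-test.

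**With loss (simulation, 4,000 trials per setting, σ = 1).** SE of the week-16 difference:

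| ρ | Loss | Change t-test | ANCOVA, week-16 observed | Likelihood with week 8 | Total reduction | Added by week 8 |
|---|---|---|---|---|---|---|
| 0.5 | 10% | 0.386 | 0.340 | 0.340 | 11.9% | 0.0% |
| 0.5 | 20% | 0.409 | 0.359 | 0.357 | 12.7% | 0.6% |
| 0.7 | 10% | 0.297 | 0.281 | 0.279 | 6.1% | 0.7% |
| 0.7 | 20% | 0.317 | 0.300 | 0.296 | 6.6% | 1.3% |

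A repeat simulation gave total reductions of 11-12% at ρ = 0.5 and 6-8% at 0.7. At 10-20% loss the total is about 17% at ρ = 0.3, 4-5% at 0.8 and about 2% at 0.9. At 0.9 baseline adjustment supplies little of it, as the 0.7% in the first table shows.

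**Why week 8 adds so little.** Given baseline, the week-8 and week-16 scores have partial correlation r = ρ/(1 + ρ), which is 0.33 at ρ = 0.5 and 0.41 at 0.7. With a fraction f lost, the large-sample variance ratio is 1 − r²f. At f = 0.2 and ρ = 0.7 this is 1 − 0.17 × 0.2 = 0.966, so the SE falls by 1.7% before small-sample loss. At f = 0 it falls by nothing.

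**Bias (illustration, 20,000 runs per scenario).** Suppose the 1, 2 or 3 worst week-8 responders in one arm only have no week-16 score. The difference among those observed is then biased by 0.06, 0.11 or 0.16 SD of the change if the week-8 and week-16 changes correlate at 0.5, and by 0.09, 0.16 or 0.23 SD at 0.7. Using week 8 brings the bias to about zero. This selection is deliberately severe.

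**The case against.** A t-test on change is unbiased under randomisation with complete data, and these are secondary outcomes in a pilot. Both points stand. This is a matter of efficiency, not validity.

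A reader might infer more, in three ways that the documents do not support.

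- *The plan discards data and breaks its own intention-to-treat rule.* Section 8 is silent on missing values and does not state a complete-case analysis. The conflict with Section 8.1 arises only if a dosed participant lacks a week-16 value and nothing is imputed. Participants who stop at or after 8 weeks undergo the Week 16 procedures and could enter the t-test if the plan said how.
- *The unused week-8 scores are the main loss.* At correlations of 0.5 to 0.7 they account for 0 to 1.3% of SE. A plain ANCOVA captures nearly all the gain. The simulated loss is also after week 8, so it does not measure what is lost from participants who stop earlier.
- *Everyone who stops before week 8 supplies a week-8 score.* The Week 8 procedures are done at discontinuation, which may be much sooner. RCS comes from a 7-day diary (Section 7.5.8) whose time points are not listed there, so a diary week around an unscheduled stop is not assured.

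Nor does a mixed model fully meet the intention-to-treat statement. With baseline as a covariate, anyone with no post-baseline score still contributes nothing.

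**Conclusion.** The point holds as a free improvement of low severity, for RCS and Raynaud VAS. The stated t-test is less precise than a baseline-adjusted estimate by roughly 12-13% of SE at correlation 0.5 and 6-7% at 0.7, with about 17% at 0.3 and about 2% at 0.9. These sizes rest on assumed correlations, equal SDs across visits and assumed loss of 10-20%. Up to 0.7, nearly all the gain is baseline adjustment and does not depend on dropout.

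The case for week 8 is retention of participants and protection against bias when loss depends on the week-8 response. Its precision gain is about 1% or less, and zero without dropout. The intention-to-treat statement would be approached, not fully met. RHI and brachial FMD are not measured at week 8, so that part cannot extend to them.

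**What to change.** In Section 8.2.2, replace the t-test for RCS and Raynaud VAS with an estimate of the week-16 treatment difference and its 95% CI from a model with the baseline score as a prespecified covariate, whether or not baseline imbalance is seen. Either form will do:

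- ANCOVA on the week-16 score; or
- a mixed model with weeks 8 and 16 as responses, treatment-by-visit terms and a small-sample degrees-of-freedom correction.

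The second is preferable if any week-16 scores are missing. Add a rule that places early-termination assessments (Section 7.1.2.5) by their actual timing, and state the missing-data assumption. State also that participants with no post-baseline score do not contribute to the estimate. List the RCS diary time points in Section 7.5.8 so that they agree with the schedule.

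The cost is SAP wording, ideally settled before unblinding, and slightly more analysis work. No new data or visits are needed.

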7.3 Efficacy

Primary efficacy outcome measure:

- Change in microvascular endothelial function as measured by EndoPAT technology.

Secondary efficacy measures:

- Change in Raynaud and digital ulcer symptom and severity
- Change in microcirculatory flow assessed by laser speckle contrast imaging
- Change in macrovascular function assessed by brachial FMD
- Health related quality of life (SHAQ and PROMIS)
- To assess vascular biomarkers in the sera (VEGF, tPA, sE-Selectin, BFGF, VCAM-1, ICAM)
- To assess EPCs.
- To assess nitrite analysis

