7.5.5 Laser Speckle Contrast Imaging

For assessment of LSCI we will use the PerCam PSI system (Perimed AB, Jarfalla, Sweden), which produces a near infrared (780 nm) laser light. The backscattered light forms a random interference (speckle) pattern. Movement, as produced by circulating red blood cells, causes the speckle pattern intensity to change, thus allowing for quantification of flow. The PeriCam PSI system will be used with the camera placed 20 cm above the SSc patient's hand, which will be immobilized by a fluid support. A region of interest on the 2nd proximal metacarpophalangeal joint will be identified prior to beginning assessments. Baseline LSCI measurements will be obtained continuously beginning five minutes prior to vaso-occlusion until 5 minutes after NTG administration.

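### The analysis sentence for reperfusion peak and nadir does not clearly match the change outcomes declared in section 8.2.2, and the primary RHI outcome has the same mismatch

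*Combined protocol and SAP*

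**What the plan says.** Section 8.2.2 lists, among the secondary outcomes, "Change in reperfusion peak between the atorvastatin and placebo groups" and "Change in reperfusion nadir between the atorvastatin and placebo groups". Neither item names visits. The paragraph that follows gives the methods, and for these two outcomes it says only: "The means of reperfusion peak and nadir between groups will be calculated and a 95% confidence interval of the difference between means generated".

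The sentence before it will "compare the mean change in RCS and Raynaud VAS between weeks 16 and baseline". The sentence after it will "compare the mean change in brachial FMD between baseline and week 16 between the two treatment groups". Both specify a change and both visits.

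Sections 2 and 7.3 declare the laser speckle outcome as a change: "Change in microcirculatory flow assessed by laser speckle contrast imaging". The schedule in section 7.1.1 marks the row "Laser Speckle Contrast Imaging (ischemia and post-NTG" at baseline and at week 16, so a change can be calculated. Section 7.5.5 describes the recording but defines neither reperfusion peak nor nadir.

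The primary outcome in section 8.2.2 is the change in RHI from baseline to week 16, yet its t-test is described as comparing mean levels. The synopsis likewise declares a change in microvascular function and then plans means of EndoPAT by group. Section 8.2.2 also provides for regression adjustment, but only if baseline differences are found and only in the primary-outcome paragraph.

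**The concern.** The declared outcome and the analysed quantity should be the same thing, stated once. Here a programmer could produce three different results for peak and nadir without departing from the text: a difference in week-16 means, a difference in mean change, or, since no visit is named, something else.

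Two things are at stake. First, section 8.1 says that the purpose of all analyses is to supply effect sizes for a later phase 3 trial. Week-16 values and change scores have different standard deviations, so the choice alters the standardized effect that is carried forward, and it could be made after the data are seen. Second, with 15 per arm, chance differences at baseline can be large, and an analysis that ignores the baseline value lets part of them into the treatment comparison.

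**Working it through.** **The plan's own figure.** Section 8.4 gives a 95% interval of ±0.374 with 15 per arm. It names no outcome and no SD, so it cannot be reproduced from stated inputs. It is consistent with an SD of 0.50: 2.048 × 0.50 × √(2/15) = 0.374, with t on 28 degrees of freedom. It has no direct bearing on peak and nadir, for which no design figure is given.

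**Text comparison.**

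| Outcome | Declared as | Analysis sentence |
|---|---|---|
| RCS, Raynaud VAS | change | mean change, both visits named |
| Brachial FMD | change, both visits named | mean change, both visits named |
| Reperfusion peak, nadir | change | group means, no visit named |
| RHI (primary) | change, both visits named | mean levels |

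The link from peak and nadir to laser speckle imaging is by elimination: RHI, RCS, VAS and FMD are each named separately, and laser speckle imaging is the remaining vascular measure. The word baseline cannot safely be left implicit either, because section 7.5.5 applies it to a recording within one session: "Baseline LSCI measurements will be obtained continuously beginning five minutes prior to vaso-occlusion until 5 minutes after NTG administration".

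**Precision.** Inputs: 15 per arm with complete data (section 8.4), equal variances at the two visits (assumed), and correlation ρ between baseline and week 16 (assumed 0.3, 0.5, 0.7). The standard error relative to a comparison of week-16 means is:

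- change score: √(2(1−ρ));
- baseline-adjusted, large sample: √(1−ρ²);
- baseline-adjusted with 30 subjects: the large-sample value × √(1+1/26) = × 1.019, the expected cost of estimating the slope.

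| ρ | Week-16 means | Change score | Adjusted, large sample | Adjusted, n = 30 | Gain vs week-16 means | Gain vs change |
|---|---|---|---|---|---|---|
| 0.3 | 1.000 | 1.183 | 0.954 | 0.972 | 3% | 18% |
| 0.5 | 1.000 | 1.000 | 0.866 | 0.883 | 12% | 12% |
| 0.7 | 1.000 | 0.775 | 0.714 | 0.728 | 27% | 6% |

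The adjusted analysis breaks even with week-16 means where (27/26)(1−ρ²) = 1, so ρ = √(1/27) = 0.19. It breaks even with change scores where (27/26)(1+ρ) = 2, so ρ = 52/27 − 1 = 0.93. Between these values it is more precise than both. Outside them it loses at most about 2% in standard error to the better alternative.

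**Chance imbalance.** The standard error of the baseline difference is √(2/15) = 0.365 SD. The chance of a difference above 0.5 SD in either direction is 2(1 − Φ(0.5/0.365)) = 17%. Given a 0.5 SD imbalance, the expected shift in the treatment difference is 0.5ρ for week-16 means (0.15, 0.25, 0.35 SD at ρ = 0.3, 0.5, 0.7) and 0.5(ρ−1) for change scores (−0.35, −0.25, −0.15 SD). Neither unadjusted analysis is protected.

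**Effect on phase 3 planning.** For the same mean difference, the required sample size scales with the variance. A change score has 2(1−ρ) = 1.4, 1.0 or 0.6 times the variance of the week-16 value at the three correlations.

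**The case against.** The best defence is that the sentence is shorthand. It comes directly after a list that defines the outcomes as changes, sections 2 and 7.3 say the same, and the primary outcome is written in the same loose way. On that reading, the means are means of the listed changes. This is plausible, and the documents do not rule it out. What remains is that the analysed quantity is left to inference when the neighbouring sentences spell it out. If shorthand was meant, the result is an unadjusted change score.

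A reader might infer more: that the plan discards the baseline measurement, or that its result would fail to estimate the treatment effect. The documents do not support either. The sentence names no visit, so omission of baseline is only its literal reading. Under 1:1 randomization the expected difference in week-16 means equals the expected difference in mean change, so a week-16-only comparison is unbiased. A reader might also infer that laser speckle is singled out. It differs from RCS, VAS and FMD but shares its wording problem with the primary outcome.

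It is also fair to say that restoring the change score alone does not reliably help precision: at ρ = 0.3 its standard error is 18% larger than that of week-16 means. The gains belong to baseline adjustment and depend on an assumed correlation.

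**Conclusion.** The mismatch is on the page and nothing elsewhere in the documents resolves it. It is a problem of specification, with a modest cost in precision and in exposure to chance imbalance. It is not a bias and does not affect the sample size. Because the primary RHI outcome has the same mismatch, the correction matters beyond two secondary outcomes.

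Baseline adjustment lowers the standard error by about 3% to 27% against week-16 means and by about 18% to 6% against change scores as ρ goes from 0.3 to 0.7. These figures rest on the assumed correlation, equal variances at the two visits, complete data on 15 per arm, and the inferred link of peak and nadir to laser speckle imaging. Whichever reading was intended, the change is a free improvement.

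**What to change.** Replace the peak and nadir sentence in section 8.2.2 with wording such as: *Reperfusion peak and nadir, derived from laser speckle contrast imaging, will each be compared between groups at week 16 by linear regression with the value at the baseline visit as covariate. The adjusted difference and its 95% confidence interval will be reported.*

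This keeps the declared outcome. Regressing the change on group and baseline gives the same group coefficient as regressing the week-16 value on group and baseline, so the adjusted difference is also the baseline-adjusted difference in change.

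Apply the same wording to RHI in section 8.2.2 and in the synopsis, and preferably to RCS, VAS and FMD so that all outcomes are handled alike. The existing commitment to check assumptions can stay. Section 7.5.5 should say that peak and nadir come from this recording and define them.

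If the sponsor prefers to keep t-tests, the minimum repair is to specify the mean change from baseline to week 16 for peak, nadir and RHI. That removes the ambiguity but not the sensitivity to chance imbalance.

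The cost is a few sentences, with no new data or visits. The only statistical price is about 2% in standard error if the correlation proves to be near zero (against week-16 means) or near one (against change scores).

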8.2.3 Safety

Tables of adverse events and serious adverse events will be created. These will be maintained by the data manager or study statistician and reported twice yearly to the Safety Officer. The internal Safety Officer will be appointed by the Principal Investigator. These tables will include masked treatment group. This is detailed in the Safety Monitoring Plan.

